7.2. Secondary Outcome Measures

7.2.1. Visual Analog Scale (VAS) Symptom Score Change

- Name: Visual Analog Scale (VAS) Symptom Score Change
- Definition: The mean change from baseline in self-reported overall hemorrhoid symptom severity, as recorded by participants on a 0-10 Visual Analog Scale (0: no symptoms, 10: most severe symptoms).
- Time Frame: Baseline to Day 10.
- Unit of Measure: Score (0-10 scale).
- Assessment Method: Daily participant-reported diaries.

7.2.2. Symptom Resolution Rate

- Name: Symptom Resolution Rate
- Definition: The percentage of participants achieving complete resolution of all baseline hemorrhoid symptoms (i.e., composite severity score = 0) by Day 10.
- Time Frame: Measured at Day 10.
- Unit of Measure: Percentage of Participants.
- Assessment Method: Based on participant daily diaries and confirmed by clinician assessment at Day 10.

7.2.3. Reduction in Individual Symptom Scores

- Name: Mean Reduction in Individual Symptom Scores (Bleeding, Pain, Itching, Swelling)
- Definition: Mean change from baseline to Day 10 for each individual symptom (bleeding, pain, itching, swelling) as assessed by the investigator using the 0-10 scale.
- Time Frame: Baseline to Day 10.
- Unit of Measure: Score (0-10 scale).
- Assessment Method: Clinician assessment via CRFs.

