3.3. Enrollment and Sample Size

- Planned Enrollment: A total of 300 participants will be enrolled (150 in the Nimsai Herbal group and 150 in the placebo group).
- Sample Size Justification: A sample size of 150 participants per arm (total 300) provides >90% power to detect a 30% difference in hemorrhoid regression rate (assuming 50% regression in the Nimsai Herbal group vs. 20% in the placebo group) with a two-sided alpha level of 0.05. This calculation accounts for potential minor dropouts.

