3.4. Study Flow Diagram

4. Study Population

4.1. Inclusion Criteria Participants must meet all of the following criteria to be eligible for enrollment:

- Males and females aged 18 to 70 years, inclusive, at the time of signing the Informed Consent Form (ICF).
- Diagnosis of symptomatic internal hemorrhoids, clinically and endoscopically confirmed as Grade 2 or 3 according to the Goligher classification system.
- History of hemorrhoidal symptoms (e.g., bleeding, pain, itching, swelling, discomfort) persisting for more than 6 weeks prior to screening.
- Willingness and ability to provide written informed consent.
- Willingness and ability to comply with all study procedures, schedules, and follow-up requirements.
- Able to understand and communicate effectively in the local language of the study site.

4.2. Exclusion Criteria Participants will be excluded if they meet any of the following criteria:

- Diagnosis of Grade 1 or Grade 4 hemorrhoids.
- Any known anorectal malignancy or suspicion of malignancy (colorectal cancer, anal canal carcinoma, inflammatory bowel disease affecting the anorectum, severe anal fissures or fistulas requiring immediate surgical intervention).
- Active bleeding from sources other than hemorrhoids (diverticulitis, inflammatory bowel disease).
- Currently pregnant or lactating women, or women of childbearing potential not using an effective method of contraception.
- Known hypersensitivity or allergy to any component of Nimsai Herbal capsules or placebo ingredients.
- Significant systemic diseases including, but not limited to, severe cardiovascular disease (unstable angina, recent myocardial infarction), severe renal impairment (end-stage renal disease), severe hepatic dysfunction (decompensated cirrhosis), or uncontrolled diabetes mellitus (HbA1c > 9%).
- Any medical or psychiatric condition that, in the opinion of the investigator, might compromise the participant's safety, ability to complete the study, or the integrity of the study data.
- Participation in another interventional clinical trial within 30 days prior to screening or during the current study.
- Use of concurrent treatments for hemorrhoids (other oral supplements, topical creams, suppositories) within 7 days prior to screening or during the study period.
- History of hemorrhoidectomy or other invasive hemorrhoid procedures (banding, sclerotherapy) within the last 6 months.

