7.1. Primary Outcome Measure

- Name: Hemorrhoid Regression Rate
- Definition: The percentage of participants achieving a clinical response, defined as a $\geq 75\%$ reduction in their composite hemorrhoid severity score from baseline to Day 10. The composite score is derived from the sum of clinician-assessed scores for four key symptoms: bleeding, pain, itching, and swelling. Each symptom is rated on a 0-10 scale (0 = no symptom, 10 = most severe symptom), resulting in a total possible score range of 0-40.
- Time Frame: Measured at Day 10, representing the end of the intervention period.
- Unit of Measure: Percentage of Participants.

Assessment Method: Clinician assessment by blinded investigators using standardized Case Report Forms (CRFs). Investigator training will include calibration exercises to ensure consistent scoring at Nimsai Academia.

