10.3. Statistical Software and Significance Level

- Statistical analyses will be performed using validated statistical software packages (SAS, R).
- All statistical tests will be two-sided, with a significance level (α) set at 0.05.

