10.5. Secondary Outcome Analysis

- **VAS Symptom Score Change:** The mean change from baseline will be compared between groups using a Mann-Whitney U test due to potential non-normal distribution of symptom scores. The effect size will be reported as a Mean Difference with 95% CI. Baseline VAS scores may be included as a covariate in sensitivity analyses (ANCOVA).
- **Symptom Resolution Rate:** Compared between groups using a Chi-square test. The effect size will be reported as a Risk Ratio with 95% CI. Logistic regression may be used to adjust for baseline severity.
- **Individual Symptom Scores:** Mean changes will be compared using appropriate parametric (t-test) or non-parametric (Mann-Whitney U) tests based on data distribution.

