Statistical Analysis Plan (SAP): (Protocol NA-2024-01)

Official Title: Double-Blind, Placebo-Controlled, Parallel-Group Randomized Controlled Trial to Evaluate the Efficacy and Safety of Nimsai Herbal in Patients with Grade 2-3 Hemorrhoids

NCT Number: NCT07034820

Protocol Number: NA-2024-001

Document Date: October 10, 2021

Version: 2

Sponsor: Nimsai Academia Bursa, Türkiye

Principal Investigator: [name] Nimsai Academia

Center [contact]

Email: [contact]

Prepared by: Nimsai Academia Bursa, Türkiye

Submission Format: PDF/A

Confidentiality Statement: This document contains confidential information and is intended solely for authorized personnel, investigators, and regulatory authorities. Unauthorized reproduction or distribution is prohibited. No participant names or identifiable information are included.

1. Introduction

This Statistical Analysis Plan (SAP) outlines the detailed methodology for the statistical analysis of data collected during Protocol NA-2024-01, double-blind, placebo-controlled, parallel-group Randomized Controlled Trial evaluating the efficacy and safety of Nimsai Herbal in patients with Grade 2-3 hemorrhoids. This SAP is developed in conjunction with the study protocol (Protocol ID: NA-2024-01) and adheres to the principles of ICH Good Clinical Practice (GCP).

2. General Statistical Approach

- **Analysis Populations:** Analyses will be conducted on an intention-to-treat (ITT) basis, including all randomized participants regardless of treatment adherence or protocol deviations. A per-protocol (PP) sensitivity analysis will also be performed to assess the robustness of the primary findings, including only participants who completed the study as per protocol and had no major deviations.
- **Missing Data Handling:** Missing data for primary and secondary outcomes will be handled using appropriate methods, primarily multiple imputation if data are considered missing at random (MAR). Sensitivity analyses using Last Observation Carried Forward (LOCF) or complete case analysis will also be performed where appropriate.
- **Software:** Statistical analyses will be performed using validated statistical software, specifically SAS (Statistical Analysis System) or R.
- **Significance Level:** All statistical tests will be two-tailed, and a significance level of $\alpha=0.05$ will be used to determine statistical significance.

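### Individual-symptom changes are tested without baseline adjustment although eligibility allows a score of 0 on any item: the comparison is unbiased, but imprecise and hard to interpret if many lack the symptom

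*Protocol*

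**What the plan says.** Protocol section 7.2.3 sets the outcome as "Mean change from baseline to Day 10 for each individual symptom (bleeding, pain, itching, swelling"), rated by the investigator. It does not limit the outcome to participants who had the symptom at baseline. Section 7.1 fixes the floor of the scale: "Each symptom is rated on a 0-10 scale (0 = no symptom, 10 = most severe symptom").

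The symptom criterion in section 4.1 is "History of hemorrhoidal symptoms (e.g., bleeding, pain, itching, swelling, discomfort) persisting for more than 6 weeks prior to screening". The list is one of examples, and it includes discomfort, which is not among the four scored items. No single symptom and no minimum score is required.

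For the analysis, section 10.5 says: "Mean changes will be compared using appropriate parametric (t-test) or non-parametric (Mann-Whitney U) tests based on data distribution". The same section offers a baseline covariate (ANCOVA) for the VAS and logistic regression on baseline severity for symptom resolution. It offers no adjustment for the individual symptoms.

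SAP section 2 applies intention-to-treat, "including all randomized participants regardless of treatment adherence or protocol deviations". SAP section 3.2 covers only the VAS and symptom resolution, so the individual symptoms have no SAP entry. Neither document gives the baseline prevalence of any symptom, an SD, an expected effect or a power figure for these four comparisons.

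**The concern.** A participant who starts at 0 on an item cannot improve on it, but still counts in that item's mean change and in its test. Two things follow if there are many such participants.

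First, the mean difference between arms shrinks in proportion to their share. It no longer tells a clinician how much a patient with bleeding, or with itching, improves. The shrinkage differs from one symptom to the next by an amount the plan does not ask to be reported, so four results printed side by side invite a misleading reading.

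Second, mixing people who can change with people who cannot adds spread unrelated to treatment, and an unadjusted test treats that spread as noise. A real effect on a less common symptom is then easier to miss.

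**Working it through.** **Inputs from the documents.** Section 3.3: "A total of 300 participants will be enrolled (150 in the Nimsai Herbal group and 150 in the placebo group"). Section 10.3: "All statistical tests will be two-sided, with a significance level" of 0.05. Scale 0–10, with 0 meaning absent (section 7.1).

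**The plan's own power figure.** It concerns the primary outcome only: 50% v 20%, 150 per arm, stated as above 90%. The pooled rate is 0.35. The null SE is √(2 × 0.35 × 0.65 / 150) = 0.0551. The alternative SE is √((0.25 + 0.16) / 150) = 0.0523. Then z = (0.30 − 1.96 × 0.0551) / 0.0523 = 3.67, and power is 99.99%. The statement is true, but says nothing about the symptom scores.

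**Dilution of the mean.** Let p be the share with the symptom, δ the effect among them, and let the others change by 0. The difference over everyone is p × δ. A 1-point shift becomes about 0.80 once scores are floored at 0. With p = 0.6 the reported difference is 0.6 × 0.80 = 0.48.

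**Loss of precision, t-test.** Let μ and σ be the mean and SD of change among those with the symptom. The variance over everyone is pσ² + p(1 − p)μ². The noncentrality for everyone, relative to those with the symptom only, is therefore 1/√(1 + (1 − p)(μ/σ)²). Example: p = 0.6 and μ/σ = 1.25 give 1/√1.625 = 0.784. If the symptomatic-only analysis has 80% power (noncentrality 2.80), the analysis of everyone has 2.80 × 0.784 = 2.20, which is 59% power, a relative loss of 26%. With p = 0.6, μ/σ of 1 gives 18% and 1.5 gives 34%. Over p from 0.3 to 0.9 and μ/σ from 0.5 to 2, the loss runs from 1% to 62%.

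**Simulation of both named tests.** Assumptions, none of them in the documents: baseline normal (mean 5, SD 2), rounded and clipped to 1–10 for those with the symptom; change −2 on placebo and −3 on active, SD 2.2; follow-up rounded and floored at 0; those at 0 stay at 0; 150 per arm. Power is shown for all randomized v symptomatic only.

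| Without the symptom | t-test | Mann-Whitney |
|---|---|---|
| 10% | loss about 4% | 87% v 91%, loss 4–5% |
| 20% | loss about 8–10% | 77% v 87%, loss about 11–12% |
| 40% | 59% v 77%, loss about 23–24% | 51% v 75%, loss about 31–32% |

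With 2,000 runs the simulation error on a power near 50% is √(0.25/2000), about 1 point, so the losses are good to a few points.

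**A second setting, tied to the plan's rates.** Suppose each symptom's fractional reduction follows the 50% v 20% assumption for a 75% reduction. With 40% lacking the symptom, the loss is 19% (t-test) and 33% (Mann-Whitney) if the SD of fractional reduction is 0.3, 8% and 15% if it is 0.4, and 2% and 3% if it is 0.5.

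**What baseline adjustment recovers.** In the simulation at 40% lacking the symptom, ANCOVA on all randomized participants with the item's baseline score has 77% power, the same as the symptomatic-only t-test. The baseline score accounts for much of the spread between those with and without the symptom.

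**The case against.** The strongest reply is that nothing here is an error. Mean change over everyone randomized is a legitimate intention-to-treat estimand, consistent with Protocol section 10.1 and SAP section 2, and the contrast between arms is unbiased. The effect among people who had the symptom is a different quantity. No section plans a formal comparison of the four symptoms, and these are secondary outcomes for which no power is claimed. All of that stands, and it limits the point to precision and interpretation.

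The driving input is also unknown. A reader might infer that many participants will score 0 on some item. Section 4.1 permits that, but no passage shows it. For a symptom that 80–90% of participants have, the loss is small.

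Nor are those at 0 without information: they can worsen. If 20% of symptom-free placebo participants and 10% of those on active developed the symptom (assumed figures), power over everyone at 40% absent would rise from 51% to 61% for Mann-Whitney and from 60% to 68% for the t-test. This argues against dropping them from the main test.

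What the reply does not answer is that section 10.5 gives baseline adjustment to the other symptom outcomes and not to this one, where a score of 0 on a single item is easiest to have.

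**Conclusion.** The point holds as a matter of precision and interpretation for a secondary outcome. Sections 7.2.3 and 10.5 leave the analysis unadjusted and unrestricted, eligibility allows a baseline of 0 on any item, and the SAP does not fill the gap. Under the simulation's assumptions the relative power loss is about 5% at 10% absent, 8–12% at 20% absent, and about 24% (t-test) to 31% (Mann-Whitney) at 40% absent. These are illustrations that rest on assumed prevalence, effect and SD and on no new onset. The dilution of the mean needs only that some participants start at 0 and that they do not change.

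Two stronger readings are tempting. One is that the plan costs about a third of the power of both named tests. In the simulation only Mann-Whitney reaches that, and only when around 40% lack the symptom. Section 10.5 leaves the choice of test to the data distribution, and the second setting shows losses as low as 2–3% at the same prevalence. The other is that the intention-to-treat comparison is wrong and must give way to symptomatic-only tests. It is valid, and the lost power can be recovered without leaving anyone out.

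**What to change.** In section 10.5, analyse each symptom score in all randomized participants by ANCOVA with that item's Day 0 score as covariate. Add a matching SAP entry under secondary outcomes. ANCOVA is already named for the VAS, so no new method is introduced.

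Name the Day 0 score explicitly. Section 4.4 schedules a baseline composite score at the screening visit (Day −2 to Day 0) and section 8.2 schedules one on Day 0, so "baseline" alone is ambiguous. Require that it be recorded before the kit is assigned.

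Add a prespecified supplementary analysis of each symptom in participants whose Day 0 item score is at least 1, reporting the number per arm. Because the subset is defined by a pre-treatment score, the comparison within it stays randomized. ANCOVA in everyone recovers the power, but its estimate is still an average over all participants; the supplement gives the effect in those who had the symptom. Among those at 0, tabulate new onset by arm.

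The cost is wording and a little more analysis work, with no new data, visits or participants. The downside is that the supplementary analyses have a different and smaller denominator for each symptom.

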7.2.4. Clinical Utility of the War-Drill Model

- Name: Association of War-Drill Model Classification with Treatment Response
- Definition: Evaluation of the association between initial classification (War Mode vs. Drill Mode) using the Parola Phenomenon and treatment response (hemorrhoid regression, symptom resolution) in both active and placebo arms.
- Time Frame: Classification at Baseline, outcomes at Day 10.
- Unit of Measure: Statistical association (Odds Ratio).
- Assessment Method: Clinical assessment for Parola Phenomenon at screening, correlated with primary and secondary outcomes.

7.3. Safety Outcome Measures

7.3.1. Incidence of Mild Gastrointestinal Discomfort

- Name: Incidence of Mild Gastrointestinal Discomfort
- Definition: Percentage of participants reporting mild gastrointestinal adverse events (e.g., nausea, bloating, dyspepsia, mild abdominal discomfort).

- Time Frame: Baseline to Day 10.
- Unit of Measure: Incidence (%).
- Assessment Method: Daily participant diaries and direct inquiry by investigators at each visit, documented on CRFs.

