2.3. Safety Objectives

- To determine the incidence of mild gastrointestinal discomfort (nausea, bloating, dyspepsia) in both treatment groups during the 10-day intervention.
- To assess the incidence of Serious Adverse Events (SAEs) in both treatment groups during the 10-day intervention.
- To determine the incidence of participant withdrawals due to adverse events in both treatment groups during the 10-day intervention.
- To specifically monitor and report the incidence of transient diarrhea in diabetic participants during the first three days of the intervention.

3. Study Design

3.1. Overall Design This is a prospective, randomized, double-blind, placebo-controlled, parallel-group clinical trial. Participants aged 18-70 years with symptomatic Grade 2-3 internal hemorrhoids will be randomized in a 1:1 ratio to either the Nimsai Herbal group or the placebo group. The intervention period will be 10 consecutive days.

[figure not shown]

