7.3.2. Incidence of Serious Adverse Events (SAEs)

- Name: Incidence of Serious Adverse Events (SAEs)
- Definition: Percentage of participants experiencing SAEs as defined by ICH GCP guidelines (death, life-threatening event, inpatient hospitalization, persistent or significant disability/incapacity, congenital anomaly/birth defect, or any other important medical event).
- Time Frame: Baseline to Day 10.
- Unit of Measure: Incidence (%).
- Assessment Method: Continuous monitoring, immediate reporting to IRB/DSMB, and documentation on CRFs.

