7.3.3. Incidence of Withdrawals Due to Adverse Events

- Name: Incidence of Withdrawals Due to Adverse Events
- Definition: Percentage of participants discontinuing the study intervention or withdrawing from the study entirely due to an adverse event.
- Time Frame: Baseline to Day 10.
- Unit of Measure: Incidence (%).
- Assessment Method: Documented on CRFs, with reasons for withdrawal clearly recorded.

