10.6. Safety Outcome Analysis

- Incidence of Mild Gastrointestinal Discomfort, SAEs, Withdrawals: Frequencies and percentages will be presented for both groups. Comparisons will be made using Fisher's Exact test for categorical data, particularly where low event counts are expected. Risk Differences with 95% CI will be reported.
- Transient Diarrhea in Diabetic Participants: This will be reported descriptively as the number and percentage of affected participants. No formal statistical test will be applied due to expected rarity.

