3.3. Safety Outcomes

3.3.1. Incidence of Mild Gastrointestinal Discomfort

- Name: Incidence of Mild Gastrointestinal Discomfort
- Definition: Percentage of participants reporting mild gastrointestinal adverse events (e.g., nausea, bloating, dyspepsia) during the study period.
- Time Frame: Baseline to Day 10
- Statistical Test: Fisher's Exact test
- Method: Comparison of categorical incidence data between the Nimsai Herbal and placebo groups. Fisher's Exact test is chosen due to the expected low event frequencies.
- Effect Size: Risk Difference with a 95% CI.

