3.3.2. Incidence of Serious Adverse Events (SAEs) and Withdrawals Due to Adverse Events

- Name: Incidence of Serious Adverse Events (SAEs) / Incidence of Withdrawals Due to Adverse Events
- Definition: Percentage of participants experiencing SAEs or discontinuing treatment/withdrawing due to AEs.
- Time Frame: Baseline to Day 10
- Statistical Test: Fisher's Exact test (if events occur)
- Method: Comparison of incidence data between groups. If no events are observed in either group, descriptive reporting will be provided (0% incidence).
- Effect Size: Risk Difference with a 95% CI.

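### With 'mild' read as a severity grade, moderate or severe GI events that are non-serious and do not stop treatment enter no planned between-arm safety analysis

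*Protocol*

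**What the plan says.** The word 'mild' runs through the GI safety outcome in both documents.

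- Protocol 2.3 (objective): "To determine the incidence of mild gastrointestinal discomfort (nausea, bloating, dyspepsia) in both treatment groups during the 10-day intervention".
- Protocol 7.3.1 (definition): "Percentage of participants reporting mild gastrointestinal adverse events (e.g., nausea, bloating, dyspepsia, mild abdominal discomfort", from Baseline to Day 10.
- Protocol 10.6 (analysis): "Incidence of Mild Gastrointestinal Discomfort, SAEs, Withdrawals: Frequencies and percentages will be presented for both groups", with Fisher's exact test and risk differences with 95% CI.
- SAP 3.3.1: "Percentage of participants reporting mild gastrointestinal adverse events (e.g., nausea, bloating, dyspepsia) during the study period". On the test, it says: "Fisher's Exact test is chosen due to the expected low event frequencies".

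The other safety outcomes compared between arms are SAEs (Protocol 7.3.2: "Percentage of participants experiencing SAEs as defined by ICH GCP guidelines") and stopping because of an AE (Protocol 7.3.3: "Percentage of participants discontinuing the study intervention or withdrawing from the study entirely due to an adverse event"). SAP 3.3.2 takes these together: "Percentage of participants experiencing SAEs or discontinuing treatment/withdrawing due to AEs".

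Collection is broader than analysis. Protocol 11.2 has every AE recorded and moved to the CRF with a three-level severity grade (mild, moderate, severe), and the Day 10 review in Protocol 8.2 covers all AEs and their severity. Neither document plans a by-arm table of all AEs or of AEs by severity.

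**The concern.** Safety is a stated objective, and GI tolerability is its first item. A count restricted to mild events can move in the wrong direction. If the product makes GI events worse in grade, participants leave the mild category, and those who stay on treatment with a non-serious event are counted in no other comparison. The active arm could then show a lower GI incidence because its events were more severe. A reader of the results would have no planned by-arm display that reveals this, although the data needed are already recorded.

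**Working it through.** **Which events reach a between-arm safety comparison.** This takes 'mild' as the grade in Protocol 11.2.

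| Event | Mild GI outcome (7.3.1, SAP 3.3.1) | SAE (7.3.2, SAP 3.3.2) | Stopping due to an AE (7.3.3, SAP 3.3.2) |
|---|---|---|---|
| Mild GI, non-serious, treatment continues | yes | no | no |
| Moderate or severe GI, non-serious, treatment continues | **no** | **no** | **no** |
| Serious GI event | by grade | yes | if stopped |
| GI event leading to discontinuation | by grade | if serious | yes |
| Non-GI, non-serious, treatment continues | no | no | no |

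Three other provisions do not fill the second row.

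- The diabetic transient-diarrhea outcome (Protocol 7.3.4, SAP 3.3.3) is descriptive, covers one subgroup on Days 1-3, and leaves out episodes that needed intervention or withdrawal.
- Protocol 11.3 sends blinded aggregated safety data to the DSMB but specifies no between-arm analysis.
- Protocol 11.2 and the Day 10 review govern recording and review, not tabulation by arm.

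**Can the reported incidence move the wrong way?** The documents give no GI rate, so there is no GI figure to reproduce. The only design figure is power above 90% for the primary outcome (150 per arm, 50% vs 20%). It reproduces at about 0.9999 and has no bearing here. **All counts below are assumed**, active vs placebo, with 150 per arm from Protocol 3.3.

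RD = a/150 - b/150, with Wald 95% CI = RD ± 1.96 × √[p₁(1-p₁)/150 + p₂(1-p₂)/150] and two-sided Fisher p.

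*Example 1.* Moderate events 15 vs 0, mild events 8 vs 15, no participant with both grades.
- Mild only: 8/150 - 15/150 = 5.3% - 10.0% = -4.7 points (CI -10.7 to 1.3; p = 0.19).
- Any severity: (8 + 15)/150 - 15/150 = 15.3% - 10.0% = +5.3 points (CI -2.2 to 12.8; p = 0.22).

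The sign reverses, although neither comparison is conclusive.

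*Overlap in example 1.* If k of the 15 participants with a moderate event also report a mild one, the mild-only RD is (8 + k - 15)/150: -4.7 points at k = 0, 0.0 at k = 7 and +5.3 at k = 15. The any-severity RD stays at +5.3 throughout, because each participant is counted once.

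*Example 2.* Mild 8 vs 8, moderate or severe 15 vs 3, no overlap.
- Mild only: RD 0.0, p = 1.00.
- Any severity: 23 vs 11, RD = 12/150 = +8.0 points, p = 0.044.

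*Example 3, low counts.* Moderate 3 vs 0, mild 12 vs 15, no overlap.
- Mild only: -3/150 = -2.0 points, p = 0.69.
- Any severity: 15 vs 15, RD 0.0, p = 1.00.
- The moderate events alone: +2.0 points, p = 0.25. No test settles anything here, and the gain is only that the three events are visible by arm.

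**The case against.** **'Mild' may be a loose label.** No text ties Protocol 7.3.1 to the grade in 11.2. Its list of examples repeats 'mild' on one item, which would be redundant if the whole outcome were filtered by grade. The Day 1 and Day 3 entries in Protocol 8.2 ask about any GI discomfort. This reading stands as a possibility. Under it, higher-grade GI events are counted, and what remains is an undefined term and no breakdown by severity. The grade reading is still the more natural one, since the word appears in the objective, the outcome, the analysis and the SAP, and Protocol 11.2 uses it as a grade.

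**Some events are caught elsewhere.** A severe event may qualify as an SAE through the important-medical-event clause (Protocol 7.3.2, 11.1); the point is limited to non-serious events for that reason. A reader might also infer that all other non-serious AEs go wholly uncompared. That is too strong: worsening bleeding, pain, itching or swelling also feeds the individual symptom scores (Protocol 7.2.3, 10.5). Those are mean changes, not incidences, so they narrow the gap without closing it.

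**The DSMB.** A reader might infer that the DSMB sees only pooled data. Protocol 11.3 does not say so; blinded aggregates could be arm totals under masked labels. It supports only the statement that no between-arm analysis is specified there.

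**Low counts.** SAP 3.3.1 expects few events, so any added estimate will be imprecise. This stands, and it argues for displaying the higher-grade events rather than testing them separately.

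**Conclusion.** The gap is real and should be fixed, as a matter of completeness in a stated safety objective. With 'mild' taken as the recorded grade, non-serious moderate or severe GI events that do not lead to discontinuation enter no planned between-arm safety analysis, and no by-arm incidence of other non-serious AEs is planned. A shift to higher grade could then lower the reported GI incidence. On the looser reading the defect is smaller: the term is undefined and severity is not shown.

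The size cannot be estimated. It depends on event rates and on how many participants report more than one grade, and the documents give neither; the examples show only what direction is possible. Two stronger conclusions are not supported. One is that the mild-only count will mislead: with enough overlap, example 1 gives the same +5.3 points as the any-severity count. The other is that moderate-or-worse events need their own formal test: the any-severity comparison can itself detect a difference (example 2), and a by-severity table shows the rest. The primary efficacy analysis and the sample size are unaffected.

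**What to change.** In Protocol 2.3, 7.3.1 and 10.6 and SAP 3.3.1, make the compared GI outcome the number of participants with any GI AE of any severity, Baseline to Day 10. Use the risk difference with 95% CI and Fisher's exact test already planned. Keep the mild count as a breakdown, with 'mild' tied explicitly to the severity grade in Protocol 11.2.

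Add one descriptive table of all AEs by arm and worst severity per participant, with GI events shown separately, including those moderate or worse.

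The cost is wording in two documents and one extra table. The number of formal tests does not rise, because the any-severity outcome takes the place of the mild one. Protocol 11.2 already puts severity on the CRF, so no new data collection is needed. The downside is that the reported GI incidence may be higher, and estimates will be imprecise if counts are as low as the SAP expects.
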